### 5.3 Subject Enrollment

All patients requiring an intervention due to reasons detailed in this protocol are potential study candidates and shall be screened for eligibility. Every effort will be made to ensure eligibility prior to enrollment. According to ISO 14155:2020, enrollment in the study occurs at the time of informed consent; however, for the purposes of this study, only subjects who are consented and meet all the study inclusion criteria and none of the study exclusion criteria and are treated, or treatment is attempted with the study device or randomized, will be considered enrolled into the study. Therefore, the enrollment date (Day 0) will be the date of the study index procedure; the enrollment date will not be the date of informed consent for this study. Subjects who do not meet all inclusion and exclusion criteria (e.g., including: (i) operator is unable to successfully predilate the lesion; (ii) either target reference vessel diameter or target lesion length are outside the eligible parameters, etc.) will be considered an angiographic screen failure and will not be followed in the study (no data will be collected on these subjects). Subjects in whom the WRAPSODY Endovascular Stent Graft System is inserted into the vasculature and the treatment of the target lesion is attempted, but the procedure is aborted without delivery of a stent graft, will be followed through discharge for safety only and the subject will be allowed to exit the study. No additional study required assessments shall be collected. These subjects will be replaced.

Subjects randomized to PTA who experience perforation, rupture or significant dissection requiring intervention beyond PTA (i.e., requires treatment with bare metal stent, non-study stent graft, drug-eluting balloon) will followed through discharge for safety only and the subject will be allowed to exit the study. No additional study required assessments shall be collected as the subject would not be able to be assessed for study endpoints. These subjects will be replaced.

Subjects who are enrolled and treated, but who are later discovered to not meet all of the study criteria will remain in the study and complete all of the study testing and follow-up requirements. A Protocol Deviation will be completed for study subjects who are found to be ineligible after enrollment.

**Refer to Figure 6:** Enrollment Diagram:

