#### 5.4 Subject Withdrawal

Subjects may withdraw at any time from the clinical trial without jeopardy or prejudice. If a subject prematurely terminates from the study, the reason for study termination will be recorded and the results will be tabulated by number and percent for each category. If termination is a result of an adverse event or death, an Adverse Event Form will also be completed. Subjects who withdraw consent after treatment will have their data evaluated until the time of their withdrawal.

The Investigator should follow all unresolved SAEs until the events are resolved, the subject is lost to follow-up, the subject has withdrawn consent, the subject completes the study, or the adverse event is otherwise explained.

All reasonable efforts will be made to obtain complete data for all subjects; however, missing observations will occur due to lost to follow-up, withdrawal, or non-adherence with required assessments. Three (3) attempts shall be made to contact subjects who do not return for study follow-up visits. The final attempt shall include a certified letter to the subject regarding study participation. If these subjects cannot be located, they will be considered lost to follow-up. If they are contacted but refuse to return for visits, they

will be considered withdrawals. If they actively request to withdraw from the study, they will be considered withdrawals. Subjects shall be encouraged to complete a final study exit visit at the time of withdrawal to assess for safety. Data collected up to the time of loss to follow-up or withdrawal will be maintained in the study database and used for analysis purposes, as appropriate. These subjects will not be replaced.

Subjects should be withdrawn from the study by the Investigator if any of the following occur as these additional treatments prevent further analysis of patency related endpoints:

- Subject proceeds to renal transplant
- Device is explanted
- Access is abandoned

Investigator may also withdraw subjects from the study for reasons other than above, where they judge this is in the subject's best interest. Data collected up to the time subject is withdrawn from the study will be maintained in the study database and used for analysis purposes, as appropriate. These subjects will not be replaced.

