### **9.1 Analysis Population**

Intent to Treat Population: The Intent to Treat (ITT) population will include all randomized subjects in the AVF Peripheral cohort, and all subjects enrolled in the AVG Anastomosis cohort.

Modified Intent to Treat Population: The Modified Intent to Treat (mITT) population will include all ITT subjects who receive treatment.

Per Protocol Population: The Per Protocol (PP) population will include all mITT subjects who additionally met all inclusion/exclusion criteria. This is a secondary analysis set for the primary safety and effectiveness endpoints, as well as secondary endpoints.

While mITT is intended as the primary analysis set for all safety and effectiveness endpoints, the primary safety and effectiveness endpoints will additionally be evaluated in the ITT and PP analysis sets as supportive information. All subjects excluded from mITT and PP analysis sets will be described in the final study report and the reasons detailed. If the ITT and mITT analysis sets contain the same subjects, then all mITT analyses will revert to the ITT analysis set and the mITT analysis set will be eliminated.

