### **12.11 Data Management**

Standardized eCRFs will be utilized by all participating sites. Investigators are responsible for the accurate completion and timely submission of the data collected during the trial. All data from the trial will be entered into eCRFs via a secure, web-based system with password protection. Incoming data will be automatically reviewed to identify inconsistent or missing data and any adverse events. Any data issues are to be promptly addressed with the investigator by the Sponsor designee and/or data manager. Quality assurance procedures will be established to ensure that complete, accurate and timely data are submitted, that protocol requirements are followed, and that complications, adverse events and adverse device effects are correctly reported and investigated, as appropriate. Investigators are to maintain all source documents as required by the protocol, including applicable laboratory results, applicable medications, supporting medical records, and signed Informed Consent forms. The source documents will be used during the regular monitoring visits to verify information from the database against data contained on the completed eCRFs.

The Investigator must maintain detailed records on all subjects who sign the Informed Consent and begin the pre-procedure evaluation. Only subjects who are enrolled, randomized (if applicable) and treatment is attempted or completed will have data entered into the eCRFs provided by the Sponsor. All data should be entered completely and promptly. For source documents, corrections should be made in a manner

[figure not shown]

that does not obscure or eliminate the original error, by striking through the original data with one line, and initialing and dating the change, along with the reason for the change (if not obvious).

Study Exit eCRFs are completed for all enrolled and treated subjects, regardless if they did or did not complete the trial (e.g., subject discontinuation, trial termination).

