**Infection, access site:** Infection at the vascular access site, documented by lab culture or clinical evidence requiring medical treatment (irrigation, debridement, antibiotics, etc.) to resolve.

**Infection, systemic:** Systemic infection documented by positive lab culture or clinical evidence, requiring medical treatment to treat and resolve.

**Intention to Treat (ITT):** The principle of including outcomes of all subjects in the analysis who are enrolled, randomized (if applicable) and treated (attempted or completed) into the study, regardless of noncompliance, protocol deviations, or withdrawal.

**Myocardial Infarction (MI):** Evidence of myocardial necrosis in a clinical setting consistent with myocardial ischemia.

**Perforation:** Puncture of a vessel wall.

**Pseudoaneurysm:** Disruption of the vessel wall characterized by an out-pouching or pocket with swirling, flowing blood outside of the confines of the lumen.

**Reference Vessel Diameter, Proximal (RVDprox):** Diameter of normal vessel (healthy segment) immediately proximal to the treated segment.

**Reference Vessel Diameter, Distal (RVDdist):** Diameter of normal vessel (healthy segment) immediately distal to the treated segment.

**Respiratory Failure:** New onset of respiratory insufficiency that requires placement of endotracheal tube and/or pneumothorax with or without chest tube.

**Respiratory Insufficiency:** Deterioration of subject's respiratory efforts that require supportive or medical treatment.

**Restenosis:** Reoccurrence of narrowing or blockage or target lesion. Recurrence stenosis within  $\pm 10$  mm proximal and/or distal to the target lesion as measured by angiography during repeat intervention.

**Retroperitoneal Bleed:** Bleeding into the back of the abdomen from a vascular access or puncture site.

**Steal Syndrome:** Ischemic signs and symptoms (pain, diminished radial pulse, coldness, cyanosis, necrosis) produced by an access device as a result of the diversion of arterial blood flow into the AV fistula.

**Stent Fracture:** Defined as clear interruption of stent strut observed in a minimum of two projections, determined by core lab examination of X-ray images.

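### Aborted stent-graft cases and PTA bail-outs leave at discharge and are replaced, so they have no 6-month patency outcome and incomplete 30-day safety data, and no planned analysis clearly brings them back.

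*Combined protocol and SAP*

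**What the plan says.** **Exit and replacement (Section 5.3).** A subject in whom the device is inserted and treatment attempted, "but the procedure is aborted without delivery of a stent graft, will be followed through discharge for safety only", may then exit with no further assessments. A subject randomised to PTA who has a perforation, rupture or significant dissection needing more than PTA is handled the same way, and the reason given is "No additional study required assessments shall be collected as the subject would not be able to be assessed for study endpoints". For each group the section adds: "These subjects will be replaced". Ordinary withdrawals under Section 5.4 are not replaced.

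**Analysis sets.** Section 9.1 makes mITT primary: "The Modified Intent to Treat (mITT) population will include all ITT subjects who receive treatment". It does not say whether an aborted or bailed-out case has received treatment. Section 9.1 defines ITT as all randomised (AVF) or all enrolled (AVG) subjects. Section 13.0 limits ITT to subjects "who are enrolled, randomized (if applicable) and treated (attempted or completed) into the study". Section 9.1 commits to a supportive ITT analysis of the primary endpoints, while Section 9.3 only permits one.

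**Data entry (Section 12.11).** "Only subjects who are enrolled, randomized (if applicable) and treatment is attempted or completed will have data entered into the eCRFs".

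**Denominators (Sections 9.8 and 9.10).** A subject with an event counts whatever the follow-up. An event-free subject counts only with at least 150 days of follow-up for 6-month TLPP, or 23 days for safety. No imputation is planned. A tipping-point analysis is planned for the primary endpoints, with no analysis set named.

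**Withdrawal (Section 5.4).** Renal transplant, explant and access abandonment lead to withdrawal, "as these additional treatments prevent further analysis of patency related endpoints".

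**The concern.** Both exclusions happen after randomisation or AVG enrolment, and how the assigned treatment performed triggers them. They therefore select on outcome, by a different mechanism in each arm. Replacement fills the place with a subject whose procedure succeeded.

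The stated reason does not cover what the endpoints need. Reintervention, hospitalisation and death to day 30 can still be observed after an aborted delivery or a bail-out. So can later target-lesion interventions and thrombosis. How such a case counts for TLPP is a matter of definition, and the plan can settle it in advance.

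At stake is the AVG claim against fixed performance goals, where no control arm carries a matching exclusion, and the protection that an ITT analysis should give the AVF comparison. Outcomes that were never collected cannot be recovered at analysis.

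**Working it through.** **1. The plan's own figures reproduce.**
- AVF: 78% vs 60%, two-sided 0.05, 80% power, pooled chi-square without continuity correction gives 103 per arm. 103/0.85 = 121.2, so 122 per arm and 244 in total.
- AVG: exact binomial, 60% goal, 74% assumed, one-sided 0.05, n = 96. The critical value is 66 successes, attained alpha 0.0484, power 0.8995. 96/0.85 = 112.9, so 113.

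The sample-size arithmetic is not at issue.

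**2. Where these subjects go.**

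| Data or analysis | Aborted SG or PTA bail-out | Randomised, no attempt |
|---|---|---|
| eCRF data (12.11) | Yes, treatment was attempted | None |
| Safety event before discharge | Recorded; counts if in the analysis set | None |
| Event-free at discharge | Out of the safety denominator unless followed 23 days | Not available |
| 6-month TLPP | Out unless an event was recorded first | Not available |
| mITT (9.1) | Not stated | Out |
| ITT by 9.1 / by 13.0 | In / in | In / out |

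An ITT analysis can be run in name. With no imputation it drops the same subjects again.

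**3. AVG effect at the boundary, aborted cases counted as failures.** The p-value is P(X ≥ x) for X ~ Binomial(n, 0.60).
- 66/96: p = 0.048, pass
- 66/97: p = 0.064, fail
- 66/98: p = 0.082, fail
- 66/99: p = 0.105, fail
- 68/99: p = 0.047, pass

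**4. AVG type I error.** The documents give no abort rate, so f is an assumption. If the true all-enrolled rate is 60% with aborts as failures, the rate among delivered cases is 0.60/(1 − f). The error is P(X ≥ 66) for n = 96 at that rate.

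| f | Rate among delivered | Type I error |
|---|---|---|
| 0 | 60.0% | 4.8% |
| 2% | 61.2% | 7.8% |
| 3% | 61.9% | 9.8% |
| 5% | 63.2% | 15.1% |
| 10% | 66.7% | 37.7% |

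**5. AVG power if aborts count.** At f = 3%, 0.74 × 0.97 = 71.8%. With n = 99 and critical value 68, power is about 79%.

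**6. AVF.** Let f be the SG abort rate and g the PTA bail-out rate, both assumed. Counted as failures, the rates become 0.78(1 − f) and 0.60(1 − g). Power is at 103 per arm.

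| f | g | SG | PTA | Difference | Power |
|---|---|---|---|---|---|
| 0 | 0 | 78.0% | 60.0% | 18.0 | 80.2% |
| 2% | 2% | 76.4% | 58.8% | 17.6 | 77.6% |
| 3% | 5% | 75.7% | 57.0% | 18.7 | about 81% |
| 5% | 5% | 74.1% | 57.0% | 17.1 | 73.7% |
| 5% | 0 | 74.1% | 60.0% | 14.1 | 57.7% |
| 0 | 5% | 78.0% | 57.0% | 21.0 | 90.2% |

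If both arms truly sit at 60% and only SG aborts are dropped, the chance of a false finding for SG is 3.8% at f = 2% and 6.7% at f = 5%, against 2.5% nominal. If only PTA bail-outs are dropped, the bias runs the other way.

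**The case against.** **Safeguards exist.** The tipping-point analysis is meant to span all possible imputations, and Section 9.1 requires every subject excluded from mITT to be described with reasons. Both help. But a tipping point on mITT could omit exactly these subjects, and a listing does not supply outcomes.

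**The numbers may be small.** Failed predilatation is a screen failure, so the harder lesions are removed before enrolment. The AVG example also sits at the boundary: with three aborts added, only 66 or 67 successes flip, and a result near the planned 74% survives (71/99, p = 0.010). This stands, and it limits the likely size of the effect without removing its direction.

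**Counting an abort as a TLPP failure is a choice.** TLPP runs from after the procedure to the next target-lesion intervention. That is fair, and it is why the plan needs a stated rule.

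**Stronger readings that the documents do not support.**
- A reader might infer that eCRF data cover only treated subjects. Section 12.11 includes attempted treatment.
- A reader might infer that the ITT analysis is impossible. It can be run, but without the missing outcomes.
- A reader might infer that each excluded PTA rupture removes a safety event. Pre-discharge events are recorded, and the plan does not say whether a bail-out within the index procedure is a safety event.
- A reader might infer that every explant or abandonment under Section 5.4 is lost to TLPP. Many may already be target-lesion events. The loss arises only if no event was recorded and follow-up is under 150 days.

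**Conclusion.** The concern holds as an outcome-dependent gap in data collection, made worse by conflicting population definitions. The exit, the missing assessments and the replacement are explicit in Section 5.3. Sections 9.1, 9.3, 9.8, 9.10, 12.11 and 13.0 together do not guarantee an analysis that includes these subjects.

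In the AVG cohort, if aborted cases count as failures, the bias can only favour the device. One such case overturns the smallest passing result, and type I error rises from 4.8% to 7.8%, 9.8% or 15.1% at assumed abort rates of 2%, 3% or 5%. These figures rest on assumed rates and on 96 evaluable subjects.

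In the AVF cohort the size and sign depend on two unknown rates. A reader might infer that the exclusions inflate the AVF result, but the documents do not show that: at 3% aborts and 5% bail-outs, the exclusions slightly favour PTA. The safety effect cannot be quantified from the documents.

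**What to change.** - **5.3:** keep every randomised AVF subject, and every AVG subject with attempted delivery, in data collection for 30-day safety and patency. Do not replace them. This concerns data, not how the subject is treated.
- **9.1, 9.3 and 13.0:** define what receiving treatment means for aborted and bailed-out cases. Align the Section 13.0 ITT definition with Section 9.1. Make the all-randomised/all-attempted analysis of both primary endpoints mandatory, with a pre-specified rule for these cases and one analysis that counts them as TLPP failures.
- **9.8:** apply the tipping point to that same set.
- **12.11:** enter eCRFs for all randomised subjects.
- **9.10:** state how explant and access abandonment before day 150 count for TLPP, and reconcile this with Section 5.4.
- **Enrolment:** state whether subjects already replaced count toward the 244 and 113.

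**Cost:** a protocol amendment, follow-up of a few more subjects, and a slightly less favourable patency estimate. If aborts count as failures, AVG power also falls, to about 79% at n = 99 with an assumed 3%. Holding 90% at 71.8% would need about 140 evaluable subjects rather than 96. The plan should state the power it accepts.

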#### 5.4 Subject Withdrawal

Subjects may withdraw at any time from the clinical trial without jeopardy or prejudice. If a subject prematurely terminates from the study, the reason for study termination will be recorded and the results will be tabulated by number and percent for each category. If termination is a result of an adverse event or death, an Adverse Event Form will also be completed. Subjects who withdraw consent after treatment will have their data evaluated until the time of their withdrawal.

The Investigator should follow all unresolved SAEs until the events are resolved, the subject is lost to follow-up, the subject has withdrawn consent, the subject completes the study, or the adverse event is otherwise explained.

All reasonable efforts will be made to obtain complete data for all subjects; however, missing observations will occur due to lost to follow-up, withdrawal, or non-adherence with required assessments. Three (3) attempts shall be made to contact subjects who do not return for study follow-up visits. The final attempt shall include a certified letter to the subject regarding study participation. If these subjects cannot be located, they will be considered lost to follow-up. If they are contacted but refuse to return for visits, they

will be considered withdrawals. If they actively request to withdraw from the study, they will be considered withdrawals. Subjects shall be encouraged to complete a final study exit visit at the time of withdrawal to assess for safety. Data collected up to the time of loss to follow-up or withdrawal will be maintained in the study database and used for analysis purposes, as appropriate. These subjects will not be replaced.

Subjects should be withdrawn from the study by the Investigator if any of the following occur as these additional treatments prevent further analysis of patency related endpoints:

- Subject proceeds to renal transplant
- Device is explanted
- Access is abandoned

Investigator may also withdraw subjects from the study for reasons other than above, where they judge this is in the subject's best interest. Data collected up to the time subject is withdrawn from the study will be maintained in the study database and used for analysis purposes, as appropriate. These subjects will not be replaced.

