#### 4.1.2. Primary Effectiveness Endpoint

The primary outcome measure for effectiveness in the WAVE Study is Target Lesion Primary Patency (TLPP) at 6 months. Target Lesion Primary Patency defined as freedom from clinically-driven target lesion revascularization (CD-TLR) or target lesion thrombosis measured through 6 months post-procedure, which is the time interval of uninterrupted patency after study procedure to the next intervention performed on the target lesion or uncorrectable target lesion occlusion.

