### **6.6 Month 3 Follow-Up – Telephone Visit**

The following evaluations will be scheduled for **Month 3** (90 days  $\pm$  15 days) post procedure:

- Medication assessment (antiplatelets, anticoagulation medications)
- Adverse assessment, including interventions on the venous outflow circuit

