### **6.7 Month 6 Follow-Up – Clinic Visit**

The following evaluations will be scheduled for **Month 6** (180 days  $\pm$  30 days) post procedure:

- Targeted physical examination, including but not limited to:
  - Physical assessment of fistula / access circuit including, but not limited to:
    - Presence / absence of steal syndrome
    - Presence / absence of thrill
    - Presence / absence of bruit
    - Presence / absence of infection
  - Dialysis status including, but not limited to:
    - Access blood flow
    - Arterial and venous pressures
    - Ipsilateral extremity edema
    - Clot aspiration during dialysis
    - Prolonged bleeding from puncture site
    - Dialysis flow rates
- Medication assessment (antiplatelets, anticoagulation medications)
- Adverse assessment, including interventions on the venous outflow circuit

Note: In situations where investigator for the site does not oversee the subject's hemodialysis, measures shall be taken to obtain the necessary information for the applicable visits by their hemodialysis provider.

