### **6.13 Vascular Access Interventions**

In the event that a subject requires an intervention to either the target lesion or elsewhere within the access circuit, the investigational site should provide sufficient documentation regarding the clinical and physiological signs and symptoms requiring the need for interventions, including but not limited to, status of thrill, bruit, infection, decreased dialysis pump flows, limitations to effective dialysis treatment, increased venous pressures, etc. Reinterventions to the target lesion and elsewhere within the access circuit shall follow the KDOQI Guidelines (2019). Such reinterventions shall only be performed on those subjects that have a clinically relevant lesion requiring intervention for resolution of clinical symptomatology. Reinterventions on lesions that are not clinically symptomatic should be avoided until such a time that the lesion is clinically symptomatic.

Angiography should only be performed if reintervention is deemed necessary from clinical and physiological symptoms. All procedural angiograms should be recorded at the same angles and views as taken during the index procedure, where possible. All images should be taken per core laboratory manual.

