## 9.10 Analysis

For the randomized AVF Peripheral cohort, the count and percentage of subjects with TLPP at 6 months will be presented by treatment arm. The percentages will be computed as

$\hat{p}_i = 1 - \frac{n_i}{m_i}, i = T(\text{treatment}), C(\text{control})$ .  $n_i$  is the number of subjects in each treatment arm who experienced non-patency event within 180 days post procedure,  $m_i$  is the number of subjects in each

treatment arm who experienced non-patency event within 180 days or had no non-patency event but followed up for at least 150 days. The hypothesis will be tested using the chi-square test, and the differences between treatments together with a two-sided 95% confidence interval will be calculated. For the primary safety endpoint, the count and percentage of subjects with a safety event at 30 days will be presented by treatment arm. The percentages will be computed as  $\hat{p}_i = 1 - \frac{n_i}{m_i}$ ,  $i = T, C$ .  $n_i$  is the number of subjects in each treatment arm who experienced an event within 30 days post procedure,  $m_i$  is the number of subjects in each treatment arm who experienced an event within 30 days or had no event but followed up for at least 23 days. Non-inferiority on the safety endpoint will be tested using the Farrington-Manning test. The differences between treatments together with the one-sided 95% upper confidence limit will be calculated.

For the nonrandomized AVG Anastomosis cohort, a one-sided p-value will be derived based on an exact binomial test. The study device will be considered to have achieved the primary effectiveness objective if the one-sided p-value is less than 0.05. Or equivalently, the lower limit of the one-sided 95% confidence limit based on exact method is greater than 60%. The same testing methodology will be used for the primary safety endpoint in comparison to the PG of 89%.

To control the overall Type I error (two-sided  $P=0.05$  superiority and one-sided  $P=0.05$  non-inferiority) in the randomized cohorts the following fixed sequence testing procedure will be taken:

Primary effectiveness superiority; if significant at two-sided  $\alpha=0.05$ , proceed to

Primary safety non-inferiority; if significant at one-sided  $\alpha=0.05$  proceed to secondary endpoints.

The key secondary effectiveness endpoint with hypothesis testing is TLPP at 12 months (360 days). Other secondary effectiveness endpoints for hierarchical testing, in order, are:

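### Section 5.4 counts a reachable subject who declines clinic visits as withdrawn, so event outcomes that could be obtained by telephone or from records are lost

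*Combined protocol and SAP*

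**What the plan says.** Section 5.4 requires three contact attempts after a missed visit and then sorts the outcomes. Subjects who cannot be found are lost to follow-up. For those who are found, the rule opens with "If they are contacted but refuse to return for visits, they". Its consequence, which also covers subjects who ask to leave, is worded "will be considered withdrawals. If they actively request to withdraw from the study, they will be considered withdrawals". Declining to travel and asking to leave the study therefore get the same status. The section then says "Data collected up to the time of loss to follow-up or withdrawal will be maintained in the study database and used for analysis purposes", and that such subjects are encouraged to attend an exit visit and are not replaced. It does not say that a visit refuser can go on being followed in another way.

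Other sections show what the outcomes need:

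- Section 4.1.2 defines the primary effectiveness endpoint as "freedom from clinically-driven target lesion revascularization (CD-TLR) or target lesion thrombosis measured through 6 months post-procedure". ACPP (4.2) is likewise defined by interventions, thrombosis and abandonment.
- Section 6.7 lists no imaging at month 6, and 6.13 says "Angiography should only be performed if reintervention is deemed necessary from clinical and physiological symptoms".
- The telephone visits at months 3, 9 and 18 (6.6, 6.8, 6.10) each include "Adverse assessment, including interventions on the venous outflow circuit".
- For clinic visits where the investigator does not oversee dialysis, "measures shall be taken to obtain the necessary information for the applicable visits by their hemodialysis provider" (6.5, 6.7, 6.9, 6.11).
- In 9.10 an event-free subject enters the 6-month TLPP denominator only if that subject "had no non-patency event but followed up for at least 150 days". The corresponding limit for 30-day safety is 23 days. Section 9.8 plans no imputation and a tipping-point analysis. Sections 9.2 and 9.3.2 add Kaplan-Meier estimates.

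**The concern.** The plan treats telephone contact as good enough to learn of interventions at three scheduled time points, but ends all contact with a subject who can be reached and merely will not come in. The outcome of such a subject is often knowable, and the rule makes it missing.

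Two things are at stake. The first is bias. Section 6.4.3 states that neither physicians nor subjects can be blinded. Willingness to return could depend on the treatment received or on how well the access works, and refusal would then be related to arm or outcome. The denominator rule adds to this: an early refuser who has already had an event is counted, while one who has not is dropped. The second is robustness. Each unknown outcome widens the set of imputations that the tipping-point analysis must survive.

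The rule also reaches past the primary endpoint. The fixed sequence in 9.10 goes on to TLPP at 12 and 24 months and ACPP at 6, 12 and 24 months, all of which depend on continued contact.

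**Working it through.** **1. When does a refusal remove an outcome?** Windows are from 6.1, denominators from 9.10.

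- *Refusal around Day 30.* The window is day 20 to 40, and contact attempts follow a missed visit. Withdrawal at, say, day 45 (assumed) leaves 45 < 150 days. The month-3 call (day 75 to 105) is not made, and an event-free subject leaves the 6-month TLPP denominator. For safety, 45 ≥ 23, so if the contact counts as follow-up the subject stays evaluable.
- *Refusal at month 6.* The window is day 150 to 210, so contact after a missed visit normally falls at or after day 150. If it counts, the subject is evaluable for 6-month TLPP. The plan does not say whether it counts. The calls at months 9 and 18 and the 12- and 24-month endpoints are lost either way.
- *Refusal at month 12.* The 24-month endpoints are lost.

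**2. The plan's sample size, reproduced.** AVF inputs from 9.7: 78% vs 60%, two-sided 0.05, 80% power, mean rate 0.69.

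n = [1.960·√(2·0.69·0.31) + 0.842·√(0.78·0.22 + 0.60·0.40)]² / 0.18² = 102.4, so 103 per arm; 103/0.85 = 121.2, so 122. Both agree with the plan.

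AVG (exact binomial, 74% vs 60%, one-sided 0.05): at n = 96, reject at 66 or more successes, alpha 0.0484, power 89.9% (planned: 90%); 96/0.85 = 112.9, so 113.

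The 15% allowance is 0.15 × 122 = 18.3 subjects per AVF arm and 0.15 × 113 = 17.0 in AVG.

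**3. Power if part of that loss is recovered.** The recovered share is an assumption; the documents give no figure.

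| Share of the 15% recovered | AVF evaluable per arm | AVF power | AVG evaluable | AVG power |
|---|---|---|---|---|
| none | 104 | 80.6% | 96 | 89.9% |
| one third | 110 | 82.8% | 102 | 90.9% |
| two thirds | 116 | 84.7% | 107 | 92.7% |
| all | 122 | 86.5% | 113 | 93.4% |

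The AVG column is not smooth, because the exact test is discrete: n = 101 gives 88.1% and n = 104 gives 88.7%, both below the value at 96.

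**4. How much could be recovered?** Part of the loss will be deaths. Section 1.2 cites 20–25% one-year mortality on hemodialysis. At constant hazard, the share dead by day 150 is 1 − 0.80^(150/365) = 9% to 1 − 0.75^(150/365) = 11%. That is an upper guide, since eligibility requires a life expectancy of at least 12 months. It would leave 15 − 11 = 4 to 15 − 9 = 6 points for all other causes, or 27% to 40% of the allowance. On this guide the one-third row is plausible and the rows below it are not.

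**5. Tipping-point illustration for AVF.** Assume the observed rates equal the planned ones, with equal loss in each arm, 122 per arm after imputation, and the uncorrected chi-square test. A cell is one combination of imputed successes in the two arms.

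| Missing per arm | Observed, SG vs PTA | Cells still showing superiority | Worst case |
|---|---|---|---|
| 18 | 81/104 vs 62/104 | 258 of 361 (71%) | 81/122 vs 80/122, p = 0.89 |
| 12 | 86/110 vs 66/110 | 141 of 169 (83%) | 86/122 vs 78/122, p = 0.28 |
| 6 | 90/116 vs 70/116 | 48 of 49 (98%) | 90/122 vs 76/122, p = 0.055 |

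The percentages count combinations and are not probabilities.

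**The case against.** The best defence is that the rule is transparent and its cost is provided for. Reasons for termination are tabulated, 5.4 promises all reasonable efforts to obtain complete data, 12.5 treats a missed office visit as a deviation, and the sample size allows for 15% non-evaluable subjects. The rule can be read as applying only to someone who refuses visits altogether. This narrows how often it applies, but gives a site no alternative to withdrawal once a reached subject declines to return. The general promise does not override the specific classification.

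It can also be said that a telephone report does not establish TLPP. That is right: 6.13, 7.3.1 and 12.10 require clinical documentation and CEC adjudication of interventions. But those records come from the treating facility and do not depend on the subject attending a study visit. The dialysis-provider note is limited to sites that do not oversee dialysis and does not mention intervention dates, so the records route would have to be extended.

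Table 9 and section 6.12 are not visible, and consent pages were removed. A missed-visit provision could sit there, so its absence cannot be confirmed.

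A reader might infer more than the text supports:

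- *That an event-free subject reached in month 6 drops out of the 6-month analysis because the last completed assessment was the month-3 call.* Section 5.4 keeps data up to withdrawal, and 9.10 asks for days of follow-up and not a completed visit. The plan is silent on whether the contact counts.
- *That 30-day safety is materially affected.* Contact after a missed Day 30 visit normally falls after day 23.
- *That a tipping-point check is all the plan has against missing data.* Kaplan-Meier estimates are also planned for 6- and 12-month TLPP. They use follow-up to censoring, but rely on censoring being unrelated to outcome, which is the point in doubt.

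**Conclusion.** The concern holds in a limited form. Section 5.4, as written, discards outcomes that could be obtained with methods the plan largely uses already. The effect is clearest for 6-month TLPP after refusal around Day 30, and for the tested 12- and 24-month TLPP and ACPP after a later refusal.

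It is not a power problem. A reader might infer that the trial is underpowered, but the 85% compliance allowance already covers the loss, and recovering a third of it would add about 2 points of AVF power. The benefit is less potential for arm-related missingness and a sturdier tipping-point result: in the illustration, going from 18 to 12 unknown outcomes per arm raises the combinations that keep superiority from 71% to 83%.

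These sizes rest on the planned rates and an assumed recovered share. The documents do not say how many losses would be reachable refusers, and they contain no evidence that refusal will differ by arm. The change is worth making because it is cheap; its absence would not invalidate the trial.

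**What to change.** In 5.4, separate declining visits from withdrawing consent. Suggested text: *Subjects who decline clinic visits but do not withdraw consent remain in the study. Each missed clinic visit is converted to a telephone visit. Where consent allows, dates of intervention, thrombosis and access abandonment are obtained from treating-provider and dialysis records, and reported interventions are documented and sent to the CEC as for any other subject. Among subjects who decline visits, only those who withdraw consent to further contact and record access are classed as withdrawn.*

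In 9.8 and 9.10, state that the date of such a contact or record check counts as follow-up time toward the 150-day and 23-day limits and the corresponding limits at 12 and 24 months. If Table 9 or 6.12 already has a missed-visit provision, refer to it from 5.4.

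The cost is one protocol paragraph, one sentence in each of the two analysis sections, and possibly a change to the consent wording on record access. The existing telephone visit content can be used. Physical-examination fields and some dialysis-status fields will be blank for converted visits; the definitions of TLPP, ACPP and 30-day safety do not require them. Treatment, endpoints and tests do not change.
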